6.10.3. Data Analyses

For all analyses, testing the primary and secondary objectives of this study, our measures of interest will be measured continuously and entered into linear regression or linear mixed-models analyses as appropriate. For each objective, as we have noted earlier, we will first analyze the data cross-sectionally within Wave 3 to determine whether tau SUVr is related with our dependent variables. A test-wise alpha of 0.05 will determine finding significance regarding research hypotheses, and post hoc analyses will be corrected for family-wise error using the multi-stage Holm-Bonferroni method (Holm, 1979). Then we will model changes from Waves 1 - 3 in endpoints and their relationship to tau at Wave 3.

- **6.10.3.1.** Our primary objective, to determine the time course of tau deposition with age, will be first assessed by computing a linear regression between the AV-1451 SUVr in each of our temporal regions of interest with participant age. Next, we will determine whether this relationship is better fit by a quadratic, exponential, or growth model. We predict that tau accumulation will accelerate in old age, thus supporting a non-linear rate of deposition.
- **6.10.3.2.** A linear mixed-model analysis will be used to relate our continuous SUVr measure of amyloid deposition with the SUVr for tau deposition in each of our temporal ROIs. An amyloid SUVr x time of testing interaction term will be used to predict changes in tau SUVr. We predict that increased amyloid burden will be associated with accelerated tau deposition.
- **6.10.3.3.** To determine differences in cognitive, structural, and functional decline between those with and without tau and amyloid pathology, we will perform multiple linear mixed-model analyses. All variables of interest will be included as continuous measures. Tau SUVr x time and amyloid SUVr x time interaction terms will be entered in these models to predict how amyloid and tau pathology predicts longitudinal changes in our cognitive, structural, and functional measure of interest. In line with recent research, we predict tau burden in particular to be strongly associated with more rapid structural and cognitive decline.
- **6.10.3.4.** Similar to section 6.10.3.3, relationships between estimated tau deposition (SUVr) with hippocampal volume and cortical thickness will be estimated by entering these variables as continuous measures in linear mixed-model analyses with interaction terms including time of scanning/testing. We hypothesize that elevated tau SUVr will be associated with more steep declines in hippocampal volume and cortical thickness.
- **6.10.3.5.** To examine the joint effect of tau and amyloid, these variables will be multiplied to form an interaction term (tau SUVr x amyloid SUVr x time) that will be entered in a linear mixed-model analysis to predict longitudinal changes in cognitive, structural, and functional measures.

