study eight years earlier. This population of subjects is critical to study because pathology for Alzheimer's disease starts long before clinically observable effects develop. The timing of tau development relative to amyloid is not well understood. The Wave 3 data will provide us the ability to relate tau aggregation in Wave 3 to magnitude of amyloid deposition both during Wave 3 and across the previous 8 - 10 years. We can also connect tau deposition in Wave 3 to present cognitive function and magnitude of decline over 8 - 10 years.

While [¹⁸F]AV-1451 was not available and no tau scanning was done for Wave 1 in the DLBS, we were able to conduct 60 [¹⁸F]AV-1451 PET scans in DLBS on 60 Wave 2 participants as part of a clinical trial by Avid Radiopharmaceuticals. During Wave 3 (the focus of the present protocol), we propose to manufacture [¹⁸F]AV-1451 via the UTSW Cyclotron and Radiochemistry Program. We will administer one dose to up to 125 participants in Wave 3. This portion of the study is important because it will allow us to assess longitudinal changes in [¹⁸F]AV-1451 in the 60 previously tested Wave 2 participants, and its relationship to growth in amyloid and decline in cognition. Secondly, we can see whether it increases more rapidly as a function of age. Finally, it will allow us to add to the information on [¹⁸F]AV-1451's safety profile. These data, in combination with DLBS behavioral data and MRI scanning and amyloid imaging, will provide a comprehensive picture of the aging mind over a period of years, allowing us a window into maintenance of cognitive health and, for some subjects, transition towards dementia.

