6.5. STUDY OBJECTIVES

6.5.1. Primary Objectives

6.5.1.1. To determine the time course of tau deposition with age and assess its relationship to changes in cognitive function over a 10-year interval by conducting tau PET scans on up to 125 adults from previous waves of the DLBS using the tau tracer [¹⁸F]AV-1451.

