6.10.1.2. Secondary Endpoints

Tau deposition will be estimated from Wave 3 data by the SUVr of [¹⁸F]AV-1451 in temporal regions (both left and right) of interest: (1) inferior temporal gyrus, (2) middle temporal gyrus, (3) superior temporal gyrus, (4) entorhinal cortex, (5) parahippocampal gyrus, and (6) fusiform gyrus. Amyloid accumulation will be measured as the SUVr value averaged across eight cortical regions: dorsal lateral prefrontal cortex, orbitofrontal cortex, lateral parietal cortex, posterior cingulate cortex, anterior cingulate cortex, precuneus, lateral temporal cortex, and occipital lobe. Both measures of tau and amyloid will be used as continuous measures rather than positive and negative dichotomy. In addition, there were 60 participants in Wave 2 who received tau imaging four years earlier. Change in tau deposition will be estimated for all returning participants who were among those that received tau imaging in both Waves 2 and 3. We also note that for all endpoints described below, we will analyze the data exclusively from Wave 3 in cross-sectional analyses, and then will also calculate change in all of these endpoints from Wave 1 to 3, and then retrospectively relate tau levels to changes in these endpoints.

- **6.10.1.2.1.** Hippocampal volume and regional cortical thickness will be estimated using FreeSurfer (ver. 5.3), with surface parcellation manually edited, when necessary, by our team of experts.
- **6.10.1.2.2.** Estimates of white matter integrity will be collected using diffusion tensor measures. For functional measures, BOLD signal from contrasts of interest using selected ROI's will be created using our

subsequent memory task and semantic judgment task and their relationship to tau deposition will be assessed. In addition, we will also use resting state data to look at how tau effects functional brain connectivity.

- **6.10.1.2.3.** Joint effects of tau and amyloid will be examined by including them as an interaction term in a linear mixed-model analysis.
- 6.10.1.2.4. Cognitive decline will be assessed using the following constructs: processing speed, episodic memory, working memory, and executive function. Scores on these constructs will be averaged across relevant DLBS tasks and standardized based on performance at the beginning of this longitudinal study (Wave 1).

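### Section 6.10.3.1 would infer accelerating tau accumulation from an age curve across people, and no model in 6.10.3 relates within-person tau change to age

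*Combined protocol and SAP*

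**What the plan says.** The primary objective (6.5.1) is "To determine the time course of tau deposition with age and assess its relationship to changes in cognitive function over a 10-year interval". For the first half of it, 6.10.3.1 plans "computing a linear regression between the AV-1451 SUVr in each of our temporal regions of interest with participant age". The second step is "Next, we will determine whether this relationship is better fit by a quadratic, exponential, or growth model". The inference to be drawn is stated next: "We predict that tau accumulation will accelerate in old age, thus supporting a non-linear rate of deposition".

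The data for this step are the Wave 3 scans. Section 6.10.1.2 states "Tau deposition will be estimated from Wave 3 data by the SUVr", and 6.10.3 says of every objective that "we will first analyze the data cross-sectionally within Wave 3". Section 6.10.1 calls the Wave 3 design cross-sectional.

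Earlier tau scans exist for 60 people, taken at Wave 2 about four years before. Section 6.10.1.2 commits to using them: "Change in tau deposition will be estimated for all returning participants" who were scanned at both waves. Section 6.4.4 gives longitudinal tau change in those 60 as a reason for Wave 3 scanning and continues "Secondly, we can see whether it increases more rapidly as a function of age".

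**The concern.** The prediction is about a rate within people. The analysis describes differences between people of different ages. A curve over ages 38 to 96 at one wave combines true change with differences between birth cohorts, and it is also shaped by who survived, returned and met the MMSE limit. The plan carries no caveat on any of these.

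At stake is the headline result of the primary objective. As written, a significant non-linear term would be reported as accelerating deposition even if nobody accelerates. The scans that bear on within-person change are partly collected already and otherwise planned, and the documents name the age question as a purpose, yet the analysis section gives no model for it.

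**Working it through.** **1. The plan's own figure.** Section 6.10.2 gives power 0.93 for r = 0.30 with N = 125. By Fisher z, two-sided 0.05: atanh(0.30) x √122 − 1.960 = 0.3095 x 11.045 − 1.960 = 1.459, so power is 0.928. It reproduces. By its own wording it covers linear relations for the secondary objectives, so it says nothing about the primary non-linear age question. For comparison, a correlation of 0.30 between tau change and age in 60 pairs gives 0.3095 x √57 − 1.960 = 0.377, power 0.65.

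**2. Which planned model could answer the age question?**
- 6.10.3.1: SUVr on age, with no person term and no time term.
- 6.10.3.2: tau change predicted by amyloid x time, with no age x time.
- 6.10.3.3 to 6.10.3.5: tau is a predictor of change in other measures.
- The general text of 6.10.3: change in the endpoints over Waves 1 to 3, related to tau at Wave 3.

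None relates within-person tau change to age.

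**3. Identification.** Write expected SUVr at age a for someone born in year b as f(a) + g(b). At a single wave b is the scan year minus a, so the fitted curve is f(a) + g(scan year − a), and its curvature is the sum of the two. In a repeat pair g(b) cancels, and the change is f(a) − f(a − 4 years). This separation holds for cohort differences in level, not for cohort differences in rate.

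**4. Size, cross-sectional test.** The documents give no SUVr variability or curvature, so these are assumptions: ages uniform over 40 to 95 (±2.75 decades), N = 125, residual SD 0.10, no within-person acceleration, cohort curvature q per decade squared. At the age extremes the bend is q x 2.75², which is 0.04 SUVr for q = 0.005 and 0.08 for q = 0.01. The SD of centred age squared is 2.75² x √(4/45) = 2.255. Non-centrality is q x 2.255 x √125 / 0.10, which is 1.26 for q = 0.005 and 2.52 for q = 0.01. The quadratic term is then significant in 24% and 71% of studies (24% and 70% by simulation). With residual SD 0.15 the figures are 13% and about 38%; with 0.20, 10% and 24%.

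**5. Size, repeat-scan test.** If the curvature q is truly within-person, change over 0.4 decade is q x (a² − (a − 0.4)²) = q x (0.8a − 0.16), so the slope on age is 0.8q per decade. Age SD is 2.75/√3 = 1.588 decades. Non-centrality is 0.8q x 1.588 x √n / SD of change. For n = 60, q = 0.01 and SD 0.05 this is 0.008 x 1.588 x 7.746 / 0.05 = 1.97. Power:

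| Pairs | SD of change | q = 0.005 | q = 0.01 | q = 0.020 |
|---|---|---|---|---|
| 60 | 0.05 | 0.16 | 0.49 | 0.97 |
| 60 | 0.08 | 0.09 | 0.23 | 0.68 |
| 37 | 0.05 | 0.12 | 0.32 | 0.85 |
| 37 | 0.08 | 0.08 | 0.16 | 0.47 |

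Simulation for 60 pairs gives 0.16, 0.48, 0.97 and 0.09, 0.23, 0.66. With no within-person acceleration the test stays at about 5%, whatever the cohort bend in level. The number of pairs is not given. The 37 is an assumption that applies the Wave 1 to Wave 2 return in the text of 6.4.1 (183/296 = 62%) to 60, and that was a different interval.

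**6. What the pairs do not remove.** A pair exists only if the person survived, returned and scored 22 or more on the MMSE. With q = 0.020 the true slope of change on age is 0.016. Under assumed logistic dropout of fast accumulators (1 or 2 log-odds per SD of change at the oldest age) it falls to 0.0136 or 0.0118, which is 15% or 26% too small.

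Wave 2 tracer came from the supplier and Wave 3 tracer is made locally. An additive SUVr shift goes into the time term. A proportional shift does not: with SUVr assumed to rise 0.05 per decade, a 5% or 10% shift creates a false slope of 0.0025 or 0.005 per decade. In 60 pairs with SD of change 0.05, that is non-centrality 0.62 or 1.23, and rejection rates of about 9% or 23%.

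**The case against.** The strongest reply is that the primary question can be read as one about age differences. The study summary in 6.3 speaks of tau across adults of different ages, 6.10.1 labels the Wave 3 design openly, 6.10.3.1 describes the regression as a first assessment, and 6.10.3 allows mixed models where appropriate. The growth model in 6.10.3.1 is undefined and could be longitudinal. This has weight, and as a description of age differences the regression is sound. But the growth model is offered as another fit to the same SUVr-on-age relation, so the curve-shape reading is likelier, and the stated prediction is about accumulation accelerating.

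A second reply is that the proposed test is weak where it matters. That stands. At the curvature that would mislead the cross-sectional test (0.005 to 0.01), 60 pairs would usually miss a real acceleration of the same size. The high power in the table belongs to curvature two to four times larger.

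A third is that the documents give no evidence of cohort curvature in tau, and that survivor loss would more plausibly flatten the old-age curve, working against the sponsor's prediction. That also stands, so the direction of any net bias is not known.

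**Conclusion.** The point holds in a bounded form. As written, 6.10.3.1 cannot separate within-person acceleration from birth-cohort differences, and 6.10.3 omits the tau-change-by-age model that 6.4.4 and 6.10.1.2 imply. This follows from the design and needs no assumed values. It should be corrected because the stated inference could give a wrong conclusion on the primary objective.

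Three stronger readings are tempting and are not supported:
- A reader might infer that the repeat scans are left unused. The plan commits to estimating tau change and models it against amyloid. What is missing is the model against age.
- A reader might infer that repeat scans would also remove survivor or MMSE selection. They would not, since each pair has passed the same selection.
- A reader might infer that the plan has a 24% to 70% false-positive rate. Those figures are conditional on assumed curvature and SD, and fall to 10% to 24% at residual SD 0.20.

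Confidence is high on the identification problem and medium on the size of every magnitude shown.

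**What to change.** In 6.10.3.1, keep the age regressions and add one linear mixed model per region for all available tau scans (Wave 3 plus Wave 2):

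SUVr = b0 + b1 age + b2 age² + b3 years + b4 (age x years) + person intercept + error,

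where age is a person-level value (for example, age at Wave 3) and years is time between that person's scans. Base any statement about within-person acceleration on b4, and describe the Wave 3 curve as age differences only. Say what the growth model means.

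State the limits alongside it:
- The expected number of repeat pairs, at most 60, with power over a range of assumed SDs.
- A non-significant b4 is not evidence against acceleration.
- Selection by survival, return and MMSE remains.
- Only an additive tracer shift between waves is absorbed by the time term, so a sensitivity analysis for a proportional shift is worth adding.

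The cost is one model of a type 6.10.3.2 already plans, and no new data. The price is that the acceleration claim rests on a smaller set of people, with wider intervals than the cross-sectional curve suggests.

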6.5.2. Secondary Objectives

- **6.5.2.1.** To assess the relationship of tau burden to hippocampal volume and cortical thickness and their contributions to predicting decline in memory and other cognitive functions.
- **6.5.2.2.** To determine whether rate of amyloid accumulation over the past 8 10-year interval predicts tau deposition.
- **6.5.2.3.** To examine the detrimental effect of tau deposits, as well as the joint effect of tau and amyloid, on changes in brain activity and cognitive function.
- **6.5.2.4.** To examine differences in cognitive, structural, and functional decline between those with and without amyloid and tau pathology.

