6.10. STATISTICAL CONSIDERATIONS

6.10.1. Study Design/Study Endpoints

This is a single-center study that uses two types of designs. First, the Wave 3 data will be analyzed separately and utilizes a cross-sectional design with age as a primary continuous variable, as well as multiple aspects of brain structure, brain function, cognitive performance, and amyloid deposition used as additional predictors of different types of cognitive function (memory, speed of processing, executive function). Then, in a second series of analyses that integrate data from Wave 1, Wave 2, and Wave 3, a retrospective-longitudinal design will be used to assess the relationship of present tau deposition to change in multiple aspects of brain structure, brain function, cognitive performance, and amyloid across time. Tau imaging agent administration is open-label, and imaging of participants will end when all eligible participants are scanned, all remaining participants have been contacted but are unable to be reached or unwilling to participate, or in the event that new safety data becomes available that indicates the study should be terminated. Study endpoints described in sections 6.5.4 and 6.5.5 are repeated below.

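### The amyloid-to-tau model (6.10.3.2) does not test the rate of amyloid accumulation that objective 6.5.2.2 asks about, and its tau-change term rests on at most 60 people, not the 125 behind the stated power

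*Combined protocol and SAP*

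**What the plan says.** Objective 6.5.2.2 opens "To determine whether rate of amyloid accumulation over the past", names an interval of 8 to 10 years, and makes tau deposition the thing predicted. Section 6.10.1.2 fixes when that outcome is measured: "Tau deposition will be estimated from Wave 3 data by the SUVr of" the tracer in six temporal regions.

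Section 6.10.3.2 first relates amyloid SUVr to tau SUVr in each region by a mixed model. It continues: "An amyloid SUVr x time of testing interaction term will be used to predict changes in tau SUVr". Its hypothesis is "We predict that increased amyloid burden will be associated with accelerated tau deposition".

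More general text points towards the objective as written. The rationale (6.4.4) expects to "relate tau aggregation in Wave 3 to magnitude of amyloid deposition both during Wave 3 and across the previous 8 - 10 years". Section 6.10.1 describes a retrospective-longitudinal design to "assess the relationship of present tau deposition to change in multiple aspects of brain structure, brain function, cognitive performance, and amyloid across time". The lead-in to 6.10.3 sets a cross-sectional step first and ends: "Then we will model changes from Waves 1 - 3 in endpoints and their relationship to tau at Wave 3".

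On tau change, 6.4.4 states that Wave 1 had no tau scans and Wave 2 had 60. Section 6.10.1.2 restricts estimated tau change to "all returning participants who were among those that received tau imaging in both Waves 2 and 3". No expected number of returning participants is given.

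Section 6.10.2 gives one power figure, 0.93 for r = 0.30, assuming tau data on all 125 people, and applies it to objectives 6.5.2.1 to 6.5.2.4 together.

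**The concern.** Three questions are in play: amyloid level with tau level, amyloid level with tau change, and amyloid change with Wave 3 tau. Objective 6.5.2.2 is the third. Section 6.10.3.2 covers the first two. In a model of tau, an amyloid-by-time term asks whether amyloid level modifies the course of tau, not whether growth in amyloid predicts tau.

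Two things are at stake. First, any of the three results could be reported as the answer to 6.5.2.2, because the plan orders the analyses without saying which one decides the objective. Second, the stated power belongs to analyses that can use 125 people. A null tau-change result could be read against 0.93 when the power of that term is clearly lower.

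**Working it through.** **Matching objectives to analyses.** Item 6.10.3.1 serves the primary objective. Item 6.10.3.3 repeats the wording of 6.5.2.4, 6.10.3.4 matches 6.5.2.1 and 6.10.3.5 matches 6.5.2.3. By elimination, 6.10.3.2 is the item for 6.5.2.2.

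| | Predictor | Outcome | People who can contribute |
|---|---|---|---|
| Objective 6.5.2.2 | rate of amyloid accumulation | Wave 3 tau | up to 125 with a tau scan, less any without usable amyloid change |
| 6.10.3.2, first sentence | amyloid SUVr | tau SUVr | up to 125 |
| 6.10.3.2, interaction term | amyloid SUVr | tau change | at most 60 with two tau scans |

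**The plan's own figure.** Inputs from 6.10.2 and 6.10.3: n = 125, r = 0.30, alpha 0.05. Fisher-z power, two-sided:

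power ≈ Φ(atanh(r)·√(n − 3) − 1.96), with atanh(0.30) = 0.3095.

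At n = 125: 0.3095 × √122 = 3.419; Φ(3.419 − 1.960) = Φ(1.459) = 0.928. A noncentral-t calculation gives 0.937 and simulation gives 0.930. The stated 0.93 reproduces. A one-sided test would give at least 0.962, so the figure is two-sided.

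**Tau change, pairs only.** The interaction is treated as one correlation of 0.30 between amyloid and within-person tau change, which is a simplification. The 50 and 40 are assumed numbers returning.

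- 60 pairs: 0.3095 × √57 = 2.337; Φ(0.377) = 0.647
- 50 pairs: 0.3095 × √47 = 2.122; Φ(0.162) = 0.564
- 40 pairs: 0.3095 × √37 = 1.883; Φ(−0.077) = 0.469

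For 80% power the requirement is ((1.960 + 0.842)/0.3095)² + 3 ≈ 85 pairs, more than the 60 that can exist.

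**Tau change, mixed model.** Let n₁ people have pairs and 125 − n₁ have only a Wave 3 scan, with equal residual variance and between-wave correlation ρ. These are assumptions, as the documents give no variance components. The variance of the interaction is proportional to (1 − ρ)²/125 + (1 − ρ²)/n₁, against 2(1 − ρ)/n₁ for pairs alone.

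With n₁ = 60 and ρ = 0.3: 0.49/125 + 0.91/60 = 0.01909, against 1.4/60 = 0.02333. Effective n = 60 × 0.02333/0.01909 = 73.3 and power is 0.738. With ρ = 0.95: 0.0025/125 + 0.0975/60 = 0.001645, against 0.1/60 = 0.001667. Effective n = 60.8 and power is 0.653.

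| Tau pairs | Pairs only | Mixed model, ρ = 0.95 to 0.3 | Simulated (4,000 runs each) |
|---|---|---|---|
| 60 | 0.65 | 0.65–0.74 | 0.63–0.74 |
| 50 | 0.56 | 0.57–0.67 | 0.58–0.66 |
| 40 | 0.47 | 0.48–0.59 | 0.47–0.58 |

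**Amyloid change against Wave 3 tau.** If r = 0.30 holds for the estimated slope, power is 0.928 at n = 125 and 0.862 at n = 100 (assumed). If r = 0.30 holds for the true slope and slope reliability is 0.6 (assumed), the observed r is 0.30 × √0.6 = 0.232, and power is 0.744 at 125 and 0.645 at 100.

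**A check on the remedy.** Illustrative assumptions: n = 125, three amyloid scans, baseline SD 1, total-change SD 0.5, error SD 0.4, tau correlated 0.5 with true baseline amyloid and not with its slope. False-positive rates for the slope at nominal 5%: 5.0% with no baseline covariate; 21 to 22% over separate simulations with observed Wave 1 amyloid as covariate (9 to 10% if the tau-baseline correlation is 0.3); 4.7% with a joint latent intercept-slope model (a single set of 1,000 runs). Observed Wave 1 amyloid shares its measurement error with the slope, which produces the inflation.

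**The case against.** The strongest reply is that the objective already has a planned analysis. The lead-in to 6.10.3 applies to every objective, and 6.10.1 and 6.4.4 name amyloid among the changes to be related to Wave 3 tau. Section 6.10.3.2 does not cite 6.5.2.2 and may have been written for the separate aim, in 6.4.4, of following tau in the 60 people scanned before. This stands in part: the intention is in the plan. But no text gives a model for it, says how the rate is computed, or says which result decides 6.5.2.2, and no other numbered item fits the objective.

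A second reply is that 0.93 is attached to objectives, not to the tau-change term, and that 125 is the right ceiling for 6.5.2.2 as worded. That is correct, and 0.93 can stand for amyloid change against Wave 3 tau if all 125 have usable amyloid change. Section 6.4.3.1 expects three amyloid scans in everyone, although 6.4.1 also recruits people who completed only Wave 1. The figure still does not describe the longitudinal term in the item that corresponds to the objective. The documents do give the ceiling of 60; what is missing is an expected number and a power for the term.

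A third reply is that a mixed model uses everyone. People with a single tau scan add some precision but no within-person tau change, and every scenario above stays well below 0.93. The mixed-model ranges and the slope reliability rest on assumed values; the 0.65 at 60 pairs rests only on the plan's own r and on treating the term as a correlation.

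Finally, age adjustment would change the power for amyloid change too. If age correlated 0.3 with both measures (assumed), the partial r would be (0.30 − 0.09)/(1 − 0.09) = 0.23, with power about 0.73 at n = 125. That is fair, and a reason to state the adjusted model when quoting power.

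**Conclusion.** The concern holds. The numbered analysis corresponding to 6.5.2.2 contains no amyloid slope and predicts tau change rather than Wave 3 tau. The analysis that would answer the objective exists only as a general intention. The stated 0.93 is right for its own inputs but does not carry over to the tau-change term: at the same r and alpha, power is 0.65 from 60 pairs, or 0.65 to 0.74 in a mixed model with between-wave correlation from 0.95 down to 0.3. It falls to 0.47 to 0.59 if only 40 of the 60 return. This is a secondary objective of an open-label observational study, and the planned data can answer it, so the fault is in the specification, not the design. It should be corrected before the analysis.

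**What to change.** 1. In 6.10.3.2, state that 6.5.2.2 is answered by relating each person's amyloid change over Waves 1 to 3 to Wave 3 tau SUVr, adjusted for age, in everyone with a Wave 3 tau scan and at least two amyloid scans. Say how the change is computed and report the n, with 125 as an upper bound. Baseline amyloid need not be a covariate. If it is adjusted for, use a joint or mixed model that allows for the error it shares with the slope, not observed Wave 1 amyloid as a simple covariate.
2. Keep the amyloid-by-time model of tau change as a separate analysis with its own n (at most 60 with two tau scans) and its own power (about 0.65 to 0.74 if all 60 return, lower otherwise), with the assumptions stated.
3. In 6.10.2, limit the 0.93 statement to analyses that can use all 125 people.
4. While editing, reconcile the mention of a third tau scan in 6.4.3.1 with the absence of tau scans at Wave 1. It does not raise the ceiling of 60.

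The cost is some SAP wording, one model on data already planned, and a less favourable stated power for tau change. No participants, scans or procedures change.

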to the developmental process of aging and cognition, fueled in part by the partial overlap of pathological markers and decline in mnemonic function observed in a substantial proportion of 'normal' aged individuals (Mohs et al., 1998; Whalley, 2002). As shown in Figure 1, a total of 296 participants were recruited for Wave 1 from 2008 to 2014 to the DLBS and they received cognitive testing, structural and functional MRI, as well as a scan for beta amyloid using the radioligand AV-45 (florbetapir F 18, also known as "[¹⁸F]AV-45"). A total of 183 returning participants were tested four years later in Wave 2, and they received the same battery (shown in Figure 2) as in Wave 1. In addition, 60 of these were also scanned with Flortaucipir F 18 (also known as "[¹⁸F]AV-1451"). [¹⁸F]AV-1451 is a newly-developed Phase II ligand that measures tau deposit in the human brain and this drug was provided to the DLBS by Avid Radiopharmaceuticals.

The objective of the current project is to manufacture [¹⁸F]AV-1451 (Flortaucipir F 18) at the University of Texas Southwestern Medical Center (UTSW) for use in Wave 3 of the DLBS. We will offer an AV-1451 PET scan to past Wave 1 and 2 participants. We will first contact those who completed Waves 1 and 2, followed by those who completed only Wave 1 until we have used the 125 doses we were allocated. Figure 3 shows the specific procedures associated with this protocol for the up to 125 participants who will receive tau imaging in Wave 3. The inclusion of tau imaging in Wave 3 will allow us to relate tau deposition in the brain to the 10-year history of amyloid deposition and cognitive decline in the DLBS participants and understand the independent and joint contributions of tau to cognitive decline and early AD at different ages.

Figure 1. Dallas Lifespan Brain Study Overview and Timeline

[figure not shown]
The DLBS is an ongoing, comprehensive study of the relationship between brain structure and function to decline in cognition across the lifespan. The focus of this protocol is noted in, "DLBS Wave 3."

DLBS Wave 1					
Study Information Measures Collecte					
•	464 Typically-healthy adults were recruited to participate Enrollment and testing occurred from 2008-2014 Ages: 30-89	-Detailed Cognitive Battery -Structural MRI -Functional MRI -Florbetapir (F18) PET Imaging -0 participants with AV-1451 PET imaging			
	DLBS \	Nave 2			
	Study Information	Measures Collected			

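### The longitudinal models specify tau × time and amyloid × time but no age × time, so as specified they do not separate a pathology effect from ageing

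*Combined protocol and SAP*

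**What the plan says.** Section 6.10.1 describes two series of analyses. The first, on Wave 3 data, "utilizes a cross-sectional design with age as a primary continuous variable". In the second, "a retrospective-longitudinal design will be used to assess the relationship of present tau deposition to change in multiple aspects of brain structure"; age is not mentioned there.

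The longitudinal models in 6.10.3 are stated through these terms:

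- 6.10.3.2 (tau change): amyloid × time of testing.
- 6.10.3.3 (cognitive, structural and functional decline): "Tau SUVr x time and amyloid SUVr x time interaction terms will be entered in these models".
- 6.10.3.4 (hippocampal volume and cortical thickness): "linear mixed-model analyses with interaction terms including time of scanning/testing".
- 6.10.3.5 (joint effect): tau × amyloid × time.

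No age term or covariate list is given for any of them, nor in the mixed-model descriptions in 6.5.5 and 6.10.1.2. Age does appear elsewhere. Section 6.10.3.1 regresses tau SUVr on age, and 6.4.4 intends to see whether tau increases faster at older ages. Neither is carried into the longitudinal models.

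The objectives served include 6.5.2.3, "To examine the detrimental effect of tau deposits, as well as the joint effect of tau and amyloid", on changes in brain activity and cognition. The background in 6.4.1 sets out the aim of separating normal from pathological ageing.

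**The concern.** On the protocol's own premises age is related to both sides of these models. Section 6.10.3.1 predicts that tau accumulation accelerates in old age, and 6.4.4 says that the cognitive functions being measured typically decline in healthy ageing. Eligible ages run from 38 to 96 (6.6.1.2), a span of 58 years. An older participant can therefore have both more tau and a steeper decline even if tau contributes nothing to the decline.

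The time variable does not deal with this. It is time of testing or scanning over some 8–10 years of follow-up, and it leaves differences in slope between younger and older people untouched.

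At stake is the interpretation of the longitudinal results: the cognitive-change part of the primary objective and objectives 6.5.2.1–6.5.2.4. The Wave 3 cross-sectional series, the tau-on-age regression and the scan-completion endpoint are not affected.

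**Working it through.** **1. The plan's own figure.** From 6.10.2 and 6.10.3: n = 125, r = 0.30, alpha 0.05 (sidedness not stated). With Fisher z, two-sided, power = Φ(z − 1.96) + Φ(−z − 1.96), where z = atanh(r) × √(n − 3 − k) and k is the number of covariates. For k = 0, power is 0.928, which reproduces the stated 0.93.

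**2. Assumptions for the false-positive rate.** The documents give no correlations, so all of these are assumed:

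- c is the tau–age correlation and also the correlation of true slope with age, 0.2 to 0.5
- amyloid–age correlation 0.3
- residual tau–amyloid correlation q, 0 or 0.3
- slope reliability ρ, 0.5 to 1.0
- linear age effects and uniform age
- tau and amyloid have no effect on slope given age

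**3. Formula.** Each person's slope is regressed on tau and amyloid, which mirrors the × time tests when waves are complete and balanced.

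- tau–slope correlation: c²√ρ
- amyloid–slope correlation: 0.3c√ρ
- tau–amyloid correlation: 0.3c + q√((1 − c²)(1 − 0.09))

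The partial correlation of tau and slope given amyloid goes into the formula of step 1 with k = 1, so that √(125 − 4) = 11.

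Example: c = 0.4, ρ = 1, q = 0. The three correlations are 0.16, 0.12 and 0.12. The partial correlation is (0.16 − 0.12 × 0.12)/(1 − 0.12²) = 0.1477, so z = 0.1488 × 11 = 1.64 and the rejection rate is 0.374.

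**4. Tau × time without age.** Lowest case: q = 0.3, ρ = 0.5. Highest case: q = 0, ρ = 1.

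| c | partial r, lowest–highest | rate by formula | rate by simulation (20,000 runs per cell) |
|---|---|---|---|
| 0.2 | 0.015–0.037 | 0.053–0.069 | 0.055–0.067 |
| 0.3 | 0.044–0.083 | 0.077–0.149 | 0.077–0.147 |
| 0.4 | 0.088–0.148 | 0.162–0.374 | 0.160–0.371 |
| 0.5 | 0.148–0.233 | 0.373–0.741 | 0.371–0.753 |

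Repeat simulations moved these limits by about one percentage point, hence the rounded ranges 5–7%, 8–15%, 16–38% and 36–75%. With age in the slope model the simulated rate is 0.047–0.052.

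**5. Unequal correlations.** With tau–age 0.3 and slope–age 0.2 the formula gives 6–9%. With 0.4 and 0.2 it gives 8–13%.

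**6. An age main effect alone does not help,** because it is the slope that is confounded. A three-wave model (times 0, 4 and 9 years, reliability 0.72, 1,500 runs) gives:

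| c | no age | age main effect only | age × time |
|---|---|---|---|
| 0.3 | 0.113 | 0.113 | 0.053 |
| 0.5 | 0.601 | 0.601 | 0.056 |

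**7. Section 6.10.3.2.** Tau change can be measured in at most 60 people, since "there were 60 participants in Wave 2 who received tau imaging four years earlier". Setting amyloid–age and tau-change–age both to c, r = c²√ρ and √(60 − 3) = 7.55. For ρ = 0.5 and 1 the formula gives 0.055 and 0.061 (c = 0.2), 0.077 and 0.105 (0.3), 0.138 and 0.230 (0.4), 0.271 and 0.487 (0.5). With age, simulation gives 0.047–0.052.

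**8. Three-way term.** With linear age effects and uniform age, rejection without age stays near 5%. With linear effects and a skewed age distribution (tau–age and slope–age 0.5, amyloid–age 0.3–0.5, ρ = 1) it is 7–12% without age and about 5% with it. If tau and decline both accelerate strongly with age (c = 0.5), the maximum is 0.241 without age, 0.161 with age × time and 0.062 with age squared × time added.

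**9. Power after adjustment.** If r = 0.30 is the age-adjusted partial correlation, power is 0.926 with one covariate and 0.924 with two. If it was meant as unadjusted, the partial correlation (leaving amyloid out) is (0.30 − c²)/(1 − c²) = 0.271, 0.231, 0.167 or 0.067 for c = 0.2, 0.3, 0.4 or 0.5. Power is then 0.86, 0.73, 0.46 or 0.11.

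**The case against.** The strongest reply is that the plan is silent on age in these models and does not exclude it. Section 6.10.3 names the terms that carry the hypotheses and gives no closed covariate list. Age is clearly in the investigators' minds: 6.4.4 looks at tau change by age, and 6.4.1 wants to "understand the independent and joint contributions of tau to cognitive decline and early AD at different ages". This stands in part. A reader might infer that the investigators decided to leave age out, or that age is planned only for cross-sectional work; the documents support neither. What they show is that age adjustment is not specified for the longitudinal models. If those models are fitted as written, the gap has consequences.

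Second, the predictions in 6.10.3.2–6.10.3.4 are worded as associations, and objective 6.5.2.2 ("To determine whether rate of amyloid accumulation over the past" 8–10 years predicts tau) does not by itself require an age-independent effect. That stands: an unadjusted tau × time term is a valid association. It does not answer 6.5.2.3, which asks about harm from tau, or the aim of separating normal from pathological ageing. The sentence in 6.4.1 on independent contributions is weak support, since its natural reading is independence from amyloid.

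Third, the size rests on assumptions. That also stands. The upper figures need strong age correlations and perfectly reliable slopes, and a uniform age distribution borrows the eligibility limits.

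**Conclusion.** The point holds as a cheap improvement. As specified, the longitudinal tau × time and amyloid × time terms mix any pathology effect with ageing. The likely direction follows from the protocol's own premises; the size does not. Under the stated assumptions the inflation is negligible at age correlations of 0.2, modest at 0.3 and large only at 0.4–0.5. It is smaller when one of the two correlations is small.

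Three stronger readings are not supported:

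- That the longitudinal results would be invalid. They remain valid associations.
- That the three-way term is safe whenever age effects are linear. A skewed age distribution is enough to bias it.
- That the stated power is wrong. The 0.93 reproduces, and it survives adjustment if r = 0.30 is the age-adjusted effect.

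**What to change.** Add Wave 1 age and age × time to the main models in 6.10.3.2–6.10.3.5. State that conclusions about tau or amyloid effects rest on the age-adjusted terms, and report the unadjusted results beside them as associations. A sensitivity analysis with age squared and age squared × time is optional; it is useful if decline as well as tau accelerates with age.

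In 6.10.2, state that r = 0.30 is the age-adjusted partial correlation. If it was meant as unadjusted, restate the power for the adjusted effect.

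The cost is protocol wording, since age is already known for every participant, and one slope-level degree of freedom per model (two in the sensitivity analysis). Adjusted estimates may be smaller and less precise.
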